5.2. Exclusion Criteria

Participants are excluded from the study if any of the following criteria apply:

Medical Conditions

1. Has persisting toxicity (NCI CTCAE v5.0 Grade > 1) related to prior therapy; however, alopecia, sensory neuropathy, hypothyroidism and rash Grade ≤ 2 are acceptable, and other Grade ≤ 2 AEs not constituting a safety risk based on the investigator's judgement are acceptable.
2. Has known symptomatic CNS metastases requiring steroids. Participants with previously diagnosed CNS metastases are eligible if they have completed their treatment and have recovered from the acute effects of radiation therapy or surgery prior to enrollment, have discontinued high dose corticosteroid treatment for these metastases for at least 2 weeks, and are neurologically stable (≤ 10 mg prednisone mg daily or ≤ 2 mg dexamethasone daily are allowed).
3. Has a diagnosis of any other malignancy within 2 years prior to enrollment, except for adequately treated basal cell or squamous cell skin cancer, or carcinoma in situ of the breast or of the cervix, low grade (Gleason ≤ 6) prostate cancer on surveillance without any plans for treatment intervention (eg, surgery, radiation, or castration), or prostate cancer that has been adequately treated with prostatectomy or radiotherapy and currently with no evidence of disease or symptoms. Other cancers not expected to affect health or survival over 2 years may be approved by the medical monitor after case review.
4. Has clinically significant (ie, active) cardiovascular disease: cerebral vascular accident/stroke (< 6 months prior to enrollment), myocardial infarction (< 6 months prior to enrollment), unstable angina, congestive heart failure (\geq New York Heart Association Classification Class II), or serious cardiac arrhythmia requiring medication.
5. Has significant neurological or psychiatric disorders that could harm participant ability or compliance with the study assessments.
6. Has an active infection requiring systemic therapy.
7. Has significant non-neoplastic liver disease (eg, cirrhosis, active chronic hepatitis).
8. Has any other major illness that, in the investigator's judgment, could substantially increase the risk associated with the patient's participation in this study.
9. Has any other diseases, metabolic dysfunction, physical examination finding, or clinical laboratory finding giving reasonable suspicion of a disease or condition that contraindicates the use of an investigational drug or that may affect the interpretation of the results or render the participant at high risk for treatment complications.
10. Has illnesses or conditions that interfere with their capacity to understand, follow, and/or comply with study procedures.

Prior/Concomitant Therapy

11. Received prior treatment with lurbinectedin or trabectedin.

12. Received prior treatment with any IP within 4 weeks of the study IP first infusion. Observational studies are permitted.
13. Received live vaccines within 4 weeks of the first dose of study treatment or plans to receive live vaccines during study participation. Administration of inactive vaccines or mRNA vaccines (for example, inactivated influenza vaccines or COVID-19 vaccines) are allowed.
14. Has major surgery \leq 4 weeks or major radiation therapy \leq 2 weeks prior to enrollment unless fully recovered. Prior palliative radiotherapy is permitted, provided it was completed at least 2 weeks prior to participant enrollment.
15. Received prior allogeneic bone marrow transplantation or solid organ transplant.
16. Patients who have progressed on prior PARPi within 3 months after initiation of PARPi treatment are excluded for the HRD-positive malignancies agnostic cohort.

Diagnostic Assessments

17. HBV or HCV infection at screening (positive HBV surface antigen or HCV RNA if anti-HCV antibody screening test positive).
18. Human immunodeficiency infection at screening (positive anti-HIV antibody).

Other Exclusions

19. Has a known or suspected hypersensitivity to any of the components of the drug product.
20. Is an investigational site staff member directly involved in the conduct of the study or a family member, site staff member otherwise supervised by the investigator, or participant who is a Jazz employee directly involved in the conduct of the study

5.3. Lifestyle Considerations

Not applicable. No restrictions are required.

5.3.1. Meals and Dietary Restrictions

The lurbinectedin population [REDACTED] detected several covariates that affected lurbinectedin [REDACTED] (Pharma Mar IB, 2022). [REDACTED] any food or fruits rich with CYP3A inhibitors or inducers (eg, grapefruit or grapefruit juice and Seville oranges) should be avoided during lurbinectedin treatment.

5.4. Screen Failures

Screen failures are defined as participants who consent to participate in the clinical study but are not subsequently entered in the study. A minimal set of screen failure information is required to ensure transparent reporting of screen failure participants to meet the CONSORT publishing requirements and to respond to queries from regulatory authorities. Minimal information includes demography, screen failure details, eligibility criteria, and any SAE.

Individuals who do not meet the criteria for participation in this study (screen failure) may be rescreened once. Rescreened participants will be automatically assigned a new participant number for every screening/rescreening event.

5.5. Criteria for Treatment Continuation

Further treatment cycles (ie, Cycle 2 and after) will be administered Q3W if the participant fulfills all the retreatment criteria within 3 days prior to the scheduled lurbinectedin infusion (Table 3) and defined in Table 4.

Table 4: Criteria for Treatment Continuation (Cycle 2 and After)

Variable	Retreatment Criteria (Day 1)
Hemoglobin ^a	≥ 9 g/dL
ANC	≥ 1.5 × 10 ⁹ /L
Platelets	≥ 100 × 10 ⁹ /L
AST/ALT	≤ 3 × ULN; for participants with documented metastatic liver disease, AST and ALT levels ≤ 5 × ULN
Total serum bilirubin	≤ 1.5 × ULN
Serum creatinine	≤ 1.5 × ULN or creatinine clearance ≥ 30 mL/min
Events of rhabdomyolysis	Withhold for Grade 2; resume at same dose if Grade ≤ 1
Other nonhematological treatment-related AEs (except isolated increased GGT and/or AP; Grade 2 asthenia, constipation, alopecia, peripheral neuropathy, or nonoptimally treated nausea and/or vomiting)	Grade ≤ 1
Active infection (including sepsis) and/or bleeding (any grade)	Absence

Abbreviations: AE = adverse event; ALT = alanine aminotransferase; ANC = absolute neutrophil count; AP = alkaline phosphatase; AST = aspartate aminotransferase; GGT = gamma-glutamyltransferase; ULN = upper limit of normal.

^a Participants may receive packed red blood cells transfusion and/or erythropoietin treatment, if clinically indicated, to increase or maintain adequate hemoglobin levels.

If a participant does not meet the requirements for treatment continuation on Cycle 2 Day 1 or subsequent cycles, reassessments will be performed at least every 48 to 72 hours for evaluation of treatment continuation. Treatment can be withheld up to a maximum of 3 weeks. Lurbinectedin dose delay and reduction rules are presented in Section 6.7.

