6.7. Study Intervention Dose Delay and Reduction Rules

For any treatment delay due to treatment-related AEs lasting more than 1 week, a dose reduction should be implemented upon recovery.

Participants may continue the study treatment at a reduced dose if they present any of the following:

- Grade ≥ 3 treatment-related nonhematological toxicity. Exceptions are Grade ≥ 3 nausea and/or vomiting not optimally treated, Grade 3 asthenia lasting ≤ 3 days, Grade 3 diarrhea lasting ≤ 2 days or not optimally treated, Grade 3 transient ALT/AST elevations that are rapidly reversible and not leading to subsequent delays, and nonclinically relevant biochemical abnormalities
- Grade 4 thrombocytopenia or Grade 3 thrombocytopenia concomitantly with Grade ≥ 3 bleeding
- Grade 4 neutropenia, any grade febrile neutropenia or neutropenia associated with infection/sepsis
 - Note: All participants receive mandatory colony-stimulating factors such as G-CSF or GM-CSF starting from Cycle 1 and during all subsequent cycles.

However, if the episode of neutropenia persists despite supportive care with G-CSF or GM-CSF, then the dose must be reduced

- Frequent or prolonged (> 1 week) dose delays due to treatment-related AEs
- Unacceptable toxicity in the judgement of the investigator

Participants who experience Grade ≥ 3 hypersensitivity reactions or Grade ≥ 3 rhabdomyolysis will be discontinued from study intervention.

Dose reduction levels are shown in Table 6.

Table 6: Lurbinectedin Dose Reduction Levels

Dose Reduction	Lurbinectedin Dose (mg/m ²)
1 (starting dose)	3.2
-1	2.6
-2	2.0

Up to 2 dose reductions are allowed per participant. Participants who continue to experience treatment-related toxicity and/or frequent dose delays after permitted dose reductions should be discontinued from the study. However, they can continue receiving the study intervention if objective clinical benefit is adequately documented by the Investigator, and upon agreement with the Sponsor. Once the dose has been reduced for an individual participant, it will not be re-escalated under any circumstance.

Participants not meeting criteria for continuation after a maximum of 3-week delay should be discontinued from the study. For delays > 3 weeks, retreatment can be considered on case-by-case basis after discussion with the medical monitor.

Details related to required follow-up laboratory tests to be performed after reporting of specific AEs are presented in [Section 8.3.4](#).

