## 5.2. Study Treatment

Participants will receive lubrinectedin 3.2 mg/m^2 IV on Day 1 of Q3W cycle. Lubrinectedin (JZP712) also known as PM01183 is a lyophilized powder for concentrate for solution for infusion. All participants will receive standard antiemetic prophylaxis before each treatment infusion.

For any treatment delay due to treatment-related AEs lasting more than 1 week, a dose reduction should be implemented upon recovery. Participants may continue the study treatment at a reduced dose if they present any of the following:

- Grade  $\geq 3$  treatment-related nonhematological toxicity. Exceptions are Grade  $\geq 3$  nausea and/or vomiting not optimally treated, Grade 3 asthenia lasting  $\leq 3$  days, Grade 3 diarrhea lasting  $\leq 2$  days or not optimally treated, Grade 3 transient ALT/AST elevations that are rapidly reversible and not leading to subsequent delays, and nonclinically relevant biochemical abnormalities
- Grade 4 thrombocytopenia or Grade 3 thrombocytopenia concomitantly with Grade  $\geq 3$  bleeding
- Grade 4 neutropenia, any grade febrile neutropenia or neutropenia associated with infection/sepsis
  - Note: Participants with Grade 4 neutropenia may continue with secondary G-CSF prophylaxis instead of dose reduction. However, if the episode is repeated despite secondary G-CSF prophylaxis, then the dose must be reduced.
- Frequent or prolonged ( $> 1$  week) dose delays due to treatment-related AEs
- Unacceptable toxicity in the judgement of the investigator.

Participants who experience Grade 3/4 hypersensitivity reactions will be discontinued from study intervention.

Jazz Pharmaceuticals, Inc.

JZP712-201 Statistical Analysis Plan - Protocol Amendment

2

Dose reduction levels are shown in Table 2. Up to 2 dose reductions are allowed per participant.

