## 8.3. Protocol Deviations

Protocol deviations will be categorized as important and non-important. Important protocol deviations will be summarized descriptively for participants with at least one important protocol deviation by cohort. The summary will include the following subtypes:

- Inclusion criteria not met
- Exclusion criteria not met
- Expired/compromised IP administered
- Subject dose not modified per protocol
- Incorrect dose of study treatment
- Failure to take action in response to apparent toxicity and failure to appropriately monitor the patient with toxicity
- Missed pregnancy test
- Failure to complete any efficacy assessments (e.g., imaging evaluations) at any timepoint

Jazz Pharmaceuticals, Inc.

JZP712-201 Statistical Analysis Plan - Protocol Amendment

2

- Failure to obtain initial informed consent, or obtaining informed consent after initiation of study procedures
- Use of an invalid/outdated consent form
- Prohibited medication taken or prohibited treatment given
- Falsification of source documentation
- Significant PI or staff misconduct or fraud
- Breach of confidentiality of participant/data privacy
- IRB approval lapse
- Non-compliance with protocol withdrawal criteria
- Significant, repeated protocol non-compliance that significantly impacts participant safety and/or the integrity of the study conduct or study data

Every subtype will be kept in the summary even if it has 0 participants. A participant with more than one important protocol deviation will be counted only once in the total number of participants with at least one important protocol deviations. A by-participant listing of all protocol deviations will be provided with deviation subtype, description, and a flag for important protocol deviation.

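### Protocol Table 4 and Section 6.7 give incompatible dosing instructions for a treatment-related Grade 2 rhabdomyolysis event held for more than 1 and up to 3 weeks

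*Protocol*

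**What the plan says.** Protocol Section 5.5, Table 4, lists the conditions for giving Cycle 2 and later cycles. Its rhabdomyolysis row says "Withhold for Grade 2; resume at same dose if Grade" is 1 or lower. The row sets no limit on the length of the hold and does not ask whether the event is related to treatment. Below the table the section adds "Treatment can be withheld up to a maximum of 3 weeks" and then "Lurbinectedin dose delay and reduction rules are presented in Section 6.7".

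Protocol Section 6.7 opens with "For any treatment delay due to treatment-related AEs lasting more than 1 week, a dose reduction should be implemented upon recovery". It lists exceptions for some Grade 3 or higher toxicities, and rhabdomyolysis is not among them. It rules out any later return to a higher dose. For Grade 3 or higher events it says that participants with "rhabdomyolysis will be discontinued from study intervention", and Protocol Section 7.1 lists the same event as a mandatory reason to stop.

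SAP Section 5.2 summarises the treatment rules and never mentions rhabdomyolysis. Its only stop for a named toxicity is "Participants who experience Grade 3/4 hypersensitivity reactions will be discontinued from study intervention".

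**The concern.** Section 5.5 sends the reader to Section 6.7 for delays and reductions, so a site is expected to apply both. If a related Grade 2 event takes more than a week to settle, Table 4 tells the site to restart at the same dose and Section 6.7 tells it to restart lower. Whichever it does, it departs from one of the two.

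Three things depend on the answer:

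- **Participants.** People with the same event may be dosed differently at different sites, and a reduction is permanent.
- **Deviations.** SAP Section 8.3 counts failure to modify a dose as the protocol requires among the important deviations. With two rules in force, the same action can be coded as compliant or as a deviation.
- **Exposure.** The number of participants with dose reductions and the relative dose intensity (SAP Section 10.1.1) change with the rule that a site follows.

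**Working it through.** The plan states no figure to reproduce. The check sets the rules side by side, followed by two short sums.

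**Inputs.** Table 4 row and 3-week limit (Protocol 5.5); over-1-week rule, dose levels 3.2, 2.6 and 2.0 mg/m², at most 2 reductions, no re-escalation (Protocol 6.7 and Table 6); discontinuation reasons (Protocol 7.1); treatment summary (SAP 5.2).

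**Rule by rule.**

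| Situation | Table 4 | Section 6.7 | Conflict? |
|---|---|---|---|
| Grade 2, hold of 1 week or less | same dose | over-1-week rule not triggered | no |
| Grade 2, judged not treatment-related | same dose | over-1-week rule not triggered | no |
| Grade 2, treatment-related, hold of more than 1 and up to 3 weeks | same dose | lower dose | yes |
| Grade 3 or higher | row addresses Grade 2 only | discontinue, as in 7.1 | no |

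Only the third line conflicts. In whole days it covers holds of 8 to 21 days, which is 21 − 7 = 14 of the 21 days allowed. That is the width of the window, not how often anyone falls in it.

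**Why the text does not settle it.** The other Table 4 rows set only a threshold for retreatment and leave the dose to Section 6.7. The rhabdomyolysis row is the only one that names the resumption dose, so the collision is confined to it. Section 6.7 speaks of any delay. The pointer from 5.5 to 6.7 gives no order of precedence.

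**Dose at stake.**

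- From 3.2 mg/m²: 1 − 2.6/3.2 = 0.1875, or 18.75% lower.
- From 2.6 mg/m²: 1 − 2.0/2.6 = 0.231, or 23.1% lower.
- From 2.0 mg/m²: both reductions are used. Table 4 still says same dose. Section 6.7 calls for a reduction that it does not permit, and Section 7.1 makes a need for more than 2 reductions a ground for stopping. Section 6.7 allows continuation where benefit is documented and the sponsor agrees.

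**SAP Section 5.2.** It carries the protocol's general item that lets participants with treatment-related Grade 3 or higher nonhematological toxicity continue at a reduced dose. The protocol adds an explicit rhabdomyolysis stop, and the SAP summary lacks it. SAP Section 3 says that the SAP is based on Protocol Amendment 2, which contains that stop.

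**The case against.** The best defence is that a specific rule overrides a general one. Amendment 2 revised Sections 5.5 and 6.7 together for rhabdomyolysis, with Grade 2 handled in Table 4 and Grade 3 or higher in 6.7. Because this is the only Table 4 row that names a dose, it could be a deliberate exception to the over-1-week rule. That reading is reasonable, but it is an inference. No sentence grants the row precedence, and Section 6.7 spells out its exceptions elsewhere without naming this one.

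It is also fair to say that Section 6.7 uses should rather than must, that the conflict needs a treatment-related Grade 2 event with a prolonged hold, and that such events will be few. Protocol Section 2.3.1 reports 2 single-agent cases, neither at 3.2 mg/m², and a small number of postmarketing reports. These points limit the size of the problem. They do not tell a site which dose to give.

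Two stronger readings are tempting and should be resisted:

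- **A reader might infer from SAP Section 5.2 that a participant kept on drug after a Grade 3 event would look compliant.** The documents do not support this. The deviation subtype in SAP Section 8.3 is "Non-compliance with protocol withdrawal criteria", so the yardstick is the protocol, and its Sections 6.7 and 7.1 agree on discontinuation. The SAP describes analyses and does not direct dosing. Its Section 5.2 is summary text that was not fully updated. It also still describes secondary G-CSF prophylaxis, where the protocol mandates primary prophylaxis from Cycle 1.
- **A reader might infer that managing rhabdomyolysis was the purpose of Amendment 2.** The summary of changes shows it as one item among many, including eligibility, mandatory G-CSF, body-surface-area dosing and analysis timing.

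**Conclusion.** The point holds as an internal inconsistency in the protocol, not as a criticism of a design choice. It covers treatment-related Grade 2 rhabdomyolysis that settles to Grade 1 or lower after a hold of more than 1 and up to 3 weeks, and nothing wider. At the starting dose the two instructions differ by 18.75%, irreversibly. For a participant already at the lowest level they may differ between continuing and stopping.

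This rests on two assumptions: that the hold in Section 5.5 and the delay in Section 6.7 are measured alike, and that the investigator attributes the event to treatment. The documents give neither a Grade 2 incidence nor a recovery time, so the number of participants affected cannot be estimated. Nothing shown here changes the response rate or its interval.

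The correction should be made because it is cheap and concerns a named safety risk. The SAP omission is a secondary alignment edit.

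**What to change.** 1. **Protocol.** Reconcile Table 4 with the first sentence of Section 6.7. State in one place whether the over-1-week rule applies to the rhabdomyolysis row, and cross-refer from the other. The sponsor decides which rule holds; this review takes no position. The statement should also cover a participant who has used both reductions, so that Sections 6.7 and 7.1 read consistently with it.
2. **SAP.** Bring the discontinuation events in Section 5.2 into line with Protocol Sections 6.7 and 7.1, or replace the list with a reference to those sections.

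The cost is about one clause in each document. No analysis, sample size or data collection changes. Once the protocol is settled, dose-modification deviations for these events can be coded against a single rule.

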5.5.1. Dose Adjustment Due to Changes in Body Surface Area

Body surface area will be recalculated on Day 1 of each treatment cycle. The dose of study intervention should be recalculated if the participant's BSA has a ≥ 10% change (higher or lower)

Jazz Pharmaceuticals
JZP712

Protocol JZP712-201-02
Amendment 02

compared with the predose Cycle 1 Day 1 value or the BSA recorded for dosing calculation at the previous cycle. Refer to [Section 6.7](#) for additional guidance regarding dose adjustment criteria.

6. STUDY INTERVENTION(S) AND CONCOMITANT THERAPY

Study intervention/treatment is defined as any investigational intervention(s), marketed product(s), or placebo intended to be administered to a study participant according to the study protocol.

6.1. Study Intervention(s)/Treatment(s) Administered

Refer to [Table 5](#) for details regarding the study intervention.

Table 5: Study Treatment/Intervention

Treatment Arm	Intervention/Treatment Name	Formulation	Unit Dose Strength(s)	Dosage Level(s)	Route of Administration	Use	Sourcing	Pkg	Labeling	Storage Conditions
1	lurbectedin (JZP712) Also known as PM01183	Lyophilized powder for concentrate for solution for infusion	4.0 mg/vial 0.5 mg/mL after reconstitution	3.2 mg/m ² every 3 weeks	Infusion/IV	Experimental	Provided centrally by the sponsor or locally by the trial site, subsidiary, or designee.	Study intervention will be provided in 4-mg/vial, sterile 30-mL, single-dose, type I clear-glass vials and labeled as required per country requirement. Child resistant packaging as required	Open labeling	If not used immediately after reconstitution or dilution, the lurbectedin solution can be stored prior to administration for up to 24 hours following reconstitution, including infusion time, at either room temperature/ambient light or under refrigeration at 2°C-8°C (36°F - 46°F) conditions.

6.1.1. Precautions During Study Treatment Administration

If extravasation of lurbinectedin occurs, immediately discontinue the infusion, remove the infusion catheter, and monitor for signs and symptoms of tissue necrosis. Administer supportive care per the institutional guidelines as needed. Administer subsequent infusion at a site that was not affected by extravasation. Consider use of a central venous catheter to reduce the risk of extravasation, particularly in patients with limited venous access. Monitor patients for signs and symptoms of extravasation during the lurbinectedin infusion.

Do not co-administer lurbinectedin and other IV drugs concurrently within the same IV line.

6.2. Preparation/Handling/Storage/Accountability

1. Further guidance and information for the final disposition of unused study interventions are provided in the Investigator Site Binder.
2. The investigator or designee must confirm appropriate temperature conditions have been maintained during transit for all study intervention received and any discrepancies are reported and resolved before use of the study intervention.
3. Only participants enrolled in the study may receive study intervention and only authorized site staff may supply or administer study intervention. All study intervention must be stored in a secure, environmentally controlled, and monitored (manual or automated) area in accordance with the labeled storage conditions with access limited to the investigator and authorized site staff.
4. The investigator, institution, or the head of the medical institution (where applicable) is responsible for study intervention accountability, reconciliation, and record maintenance (ie, receipt, reconciliation, and final disposition records).

